6.3 Recruitment methods

Healthy volunteers will be recruited by advertisement in universities or website

Total number of participants to be randomized and received at least one dose and have one post dose PK sample.	15
Number of sites	1
Enrolment period (months)	16
Number of participants/site	15
Number of participants/site/month	1

7 TREATMENT ADMINISTERED TO STUDY PARTICIPANTS

7.1 The investigational medicinal product

7.1.1 Tranexamic Acid

Patient will receive the marketed forms of tranexamic acid (Exacyl®):

- Exacyl® (Sanofi Aventis) 0.5 g/5 ml injectable solution IV
- Exacyl® (Sanofi Aventis) 1 g/10 ml oral solution

Storage conditions: each package contains 5 vials which will be stored at ambient temperature at Necker Hospital Pharmacy, Paris, France.

Labeling: each vial will be labelled for “research use only”

Dosing: Each volunteer will receive one dose tranexamic acid through each of the three routes on three separate days. The selected doses and routes are:

- Intravenous route: 1 g (2 vials x 5 mL, total volume 10 mL) will be given by in slow infusion at a rate of approximately 1 mL/min by trial personnel trained to administer IV injections.
- Intramuscular route: 1 g (2 vials x 5 mL). Each 5mL will be injected separately to the deltoid muscle of the arms or the vastus lateralis muscle of the thighs. IM injections will only be administered by trial personnel trained to administer these. Each injection will be given using the Z-track method. The Z-track is a method of administrating an IM injection that prevents the medication being tracked through the subcutaneous tissue, sealing the medication in the muscle, and minimizing irritation from the medication. Using the Z-track technique, the skin is pulled laterally, away from the injection site, before the injection; then the medication is injected, the needle is withdrawn, and the skin is released [37]. The site of each injection will be recorded.
- Oral route: 2 g (2 vials x 10 mL) will be swallowed.

7.2 Traceability information for the investigational medicinal product

The investigational medicinal products will be purchased and managed by the Pharmacy at Necker Hospital, Paris. The lot number and expiry date of each dose of drug and the inclusion number of the participant will be recorded on a Drug Accountability Log. Date, time and name of person administering each dose will be recorded.

7.3 Authorised and prohibited treatments (medicinal, non-medicinal, surgical), including emergency medications

Prohibited Medication/Class of drug:	Usage:
Any other prescription or non-prescription medication	NA

The following medications and procedures are allowed during the study:

Rescue/Supportive Medication/Class of drug:	Usage:
Any emergency drug which would be required for volunteer care	Emergency treatment

7.4 Methods for monitoring compliance with the treatment

A single dose per route (oral, intramuscular and intravenous) of TXA will be administered by investigators at the hospital. If a dose is not administered, the reason for this will be recorded in the CRF.

8 EFFICACY ASSESSMENT

8.1 Description of parameters for assessing efficacy endpoints

Due to its very high specificity, mass spectrometry is recognized as a reference method for drug analysis. Our team is experienced in mass spectrometry and has a record of publication in the development of new methods, including tranexamic acid [38-43]. Tranexamic acid will be measured in samples with liquid chromatography coupled to mass spectrometry according to an analytical method validated following the EMA guideline on bioanalytical method validation [40,43].

8.2 Anticipated methods and timetable for measuring, collecting and analysing the efficacy data

Drug concentration is collected at Visits V1, V2, V3, V4, V5 and V6: for more details see sections 5.2 and 5.3.

10 SAFETY ASSESSMENT - RISKS AND RESTRICTIONS ADDED BY THE STUDY

10.1 Safety endpoints

Safety Endpoints are:

- ✓ Number of participants with solicited local and systemic adverse events.
- ✓ Average pain score reported by participants during intramuscular administration (visual analogic scale)
- ✓ Duration of pain from intramuscular administration (hours)
- ✓ Local reaction at site of injection (redness, swelling, induration, tenderness, ecchymosis, necrosis, nerve injury, infection)
- ✓ Systemic events (fever, nausea, vomiting, seizure, diarrhoea, visual impairment)
- ✓ Vital signs (blood pressure, heart rate and respiratory rate) after administration

Number of participants reporting one or more adverse events and serious adverse events

10.2 Anticipated methods and timetable for measuring, collecting and analysing the safety endpoints

Safety Endpoints are recorded at each visit: for more details see sections 5.2 and 5.3.

- ✓ Pain is assessed by Visual Analog Scale (intensity from 0 to 9)
- ✓ Reaction at site of injection is assessed by visual inspection (measure in mm of the surface in case of reaction, and time of occurrence)

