2.5 Name and description of the investigational medicinal product(s)

Patient will receive the marketed forms of tranexamic acid:

- Exacyl® (Sanofi Aventis) 0.5 g/5 ml injectable solution
- Exacyl® (Sanofi Aventis) 1 g/10 ml oral solution.

See Section 7 for further information about the product.

2.6 Description and justification of the dosage, route of administration, administration schedule and treatment duration

Each volunteer will receive one dose of medication through each of the three routes (oral, intravenous, intramuscular), on three separate days. The selected doses are 1g for the intravenous and intramuscular routes and 2g for the oral route due to the 100% intramuscular bioavailability and 50% oral bioavailability [10].

See Section 7 for further information about the administration of the product.

2.7 Summary of the known and foreseeable benefits and risks for the study participants

There is no benefit for participants. The foreseeable risks are those related to IMP and the routes of administration. The most frequent risks associated with the administration of tranexamic acid through the intravenous, intramuscular and oral routes are:

- digestive disorders (diarrhoea, nausea, vomiting; appearing in >1/100 and <1/10 patients)
- allergic dermatitis (>1/1000 and <1/100)

Cases of visual impairment or convulsions have been reported with tranexamic acid, but only at high doses or during cardiac surgery. In the present study, the doses (1g through the parenteral routes and 2g through the oral route) are lower than doses used in routine clinical practice.

Insertion of intravenous cannula for intravenous administration of TXA and blood sampling may cause pain (common), bruising (rare), local allergic reaction secondary to disinfectant or adhesive plaster, vagal malaise and possibly infection (very rare).

Intramuscular injection procedure of a large volume may cause pain (common), Local reaction at site of injection (including Injection site redness (common), Injection site swelling (common), Injection site tenderness (common), Injection site ecchymosis (common), Injection site induration (rare), injection site necrosis (very rare), injection site nerve injury

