- **Reaction at site of injection:** Each injection site will be checked visually for local reaction and any other complications (including redness, swelling, induration, tenderness, ecchymosis, necrosis, nerve injury, infection) every fifteen minutes after administration for the first one hour then every two hours up to 8 hours after each injection and once at each subsequent visit. Reaction will be measured in millimetre, and time of occurrence will be recorded.

- Participants will have their **vital signs** (blood pressure, heart rate and respiratory rate) monitored and recorded at every fifteen minutes after administration for the first one hour then every two hours after drug administration.
- All **adverse events** and **concomitant treatments** will be recorded. The following adverse events will be elicited specifically (fever, nausea, vomiting, diarrhoea, visual impairment, seizure).

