- Blood samples for **pharmacokinetics** (*0,5 mL of venous blood in dry tube without anti-coagulant*) will be taken at the following times after drug administration:
 - T₀+ 5min (only for IV route)
 - T₀+30min
 - T₀+1h
 - T₀+2h
 - T₀+3h
 - T₀+4h
 - T₀+5h
 - T₀+6h
 - T₀+8h (only for IM and PO routes)
- **Dry Blood Spot:** At one time-point (any time-point between T₀+ 5min and T₀+8h), a capillary blood sample will be taken at a finger with a lancet and a drop of blood will be placed on Mitra[®] device. An aliquot of 200µL of whole blood will be taken and aliquoted from the venous blood sample taken at the same time.
- **Reaction at site of injection:** Each injection site will be checked visually for local reaction and any other complications (including redness, swelling, induration, tenderness, ecchymosis, necrosis, nerve injury, infection) every fifteen minutes after administration for the first one hour then every two hours up to 8 hours after each injection and once at each subsequent visit. Reaction will be measured in millimetre, and time of occurrence will be recorded.

- Participants will have their **vital signs** (blood pressure, heart rate and respiratory rate) monitored and recorded at every fifteen minutes after administration for the first one hour then every two hours after drug administration.
- All the **adverse events** and **concomitant treatments** will be recorded.

Visit V4 (=visit V3 +24h):

- **Pain assessment** using a Visual Analog Scale will be recorded at T₀+24h (+/- 1 hour). The VAS used will be the Numerical Pain Rating Scale where individuals rate their pain on a ten-point numerical scale. The scale is composed of 0 (no pain at all) to 9 (worst imaginable pain). Participants will be offered pain relief if needed in the form of simple analgesia (paracetamol).
- **Vital signs** (blood pressure, heart rate and respiratory rate) recorded at T₀+24h (+/- 1 hour).
- Blood samples for **pharmacokinetics** (*0,5 mL of venous blood in dry tube without anti-coagulant*) will be taken at T₀+24h.
- **Reaction at site of injection:** Each injection site will be checked visually for local reaction and any other complications (including redness, swelling, induration, tenderness, ecchymosis, necrosis, nerve injury, infection) at T₀+24h (+/- 1 hour). Reaction will be measured in millimetre, and time of occurrence will be recorded.
- All the **adverse events** and **concomitant treatments** are collected.

Visit V5 (=3rd drug administration):

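### The only method given for injection-site reactions is a visual check with a millimetre reading, which cannot establish tenderness or nerve injury and assesses induration poorly, so mainly tenderness risks being under-recorded.

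*Protocol*

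**What the plan says.** Section 10.1 makes local reactions a safety endpoint and names eight: "Local reaction at site of injection (redness, swelling, induration, tenderness, ecchymosis, necrosis, nerve injury, infection"). It also counts "Number of participants with solicited local and systemic adverse events". Section 4.1.2 has the same two endpoints.

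Section 10.2 states how reactions are found: "Reaction at site of injection is assessed by visual inspection (measure in mm of the surface in case of reaction, and time of occurrence"). The V1 procedure in section 5.2 agrees: "Each injection site will be checked visually for local reaction and any other complications (including redness, swelling, induration, tenderness, ecchymosis, necrosis, nerve injury, infection"). Section 5.3 repeats the visual check at V2 to V6 and adds: "Reaction will be measured in millimetre, and time of occurrence will be recorded".

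Section 5.2 also lists what participants are actively asked about: "The following adverse events will be elicited specifically (fever, nausea, vomiting, diarrhoea, visual impairment, seizure"). All six items are systemic.

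Among the expected effects of a large-volume intramuscular (IM) injection, section 2.7 lists "Injection site tenderness (common"), with induration as rare and nerve injury as very rare.

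**The concern.** The prescribed method does not fit part of its own endpoint. Tenderness is found by pressing or asking. Nerve injury shows mainly as altered sensation or strength. Induration is found by touch. A member of staff who follows the text exactly looks at the site and measures what is visible, and need neither touch it nor ask.

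This matters because the scope stated in the section 1 summary includes the safety of IM administration, and section 3.2 makes local safety by route a secondary objective. Section 2.7 names local tissue reaction as a concern with IM tranexamic acid, and section 10.3.4 acknowledges that fewer data exist for that route. An item that is listed but not looked for in a suitable way can be tabulated as absent when it was never properly assessed.

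**Working it through.** The plan gives no figure to reproduce. The check compares each listed item with the stated method, looks for another procedure that fills the gap, and then sizes what could be affected.

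**1. Item against method**

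| Reaction (10.1) | Visible? | Has a size in mm? |
|---|---|---|
| Redness, swelling, ecchymosis | Yes | Yes |
| Necrosis | Yes | Possibly |
| Infection | In part | Not as such |
| Induration | Poorly; needs touch | Yes, once felt |
| Tenderness | No | No |
| Nerve injury | No, apart from an evident motor deficit | No |

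Three of the eight items do not fit the method: two not at all, one poorly.

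**2. Other procedures that might fill the gap**

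- *Elicited events (5.2):* six systemic items and no local one, so nothing says how local events become solicited.
- *Physical examination:* the chronology table in 5.5 marks it at V0 only. Section 12.1 speaks of findings at a final visit, but neither 5.3 nor the table schedules that examination.
- *Pain score (5.2, 5.3):* a prompted 0 to 9 rating at 0, 2, 4, 6, 8 and 24 h. Site checks fall at 15, 30, 45 and 60 min, then two-hourly to 8 h, then at 24 h. Counted from dosing, that is 4 + 4 + 1 = 9 checks. A pain rating coincides with five of them (2, 4, 6, 8 and 24 h) and with none of the four in the first hour.
- *Adverse event recording (5.2 to 5.4):* all events are recorded, but no prompt for local symptoms is specified.

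**3. What could be affected in 15 volunteers**

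Input: n = 15, each receiving one IM dose (2.4, 2.6). The protocol does not define its frequency terms for injection-site reactions, so I assume: common, 1/100 to 1/10; rare, 1/10,000 to 1/1,000; very rare, below 1/10,000. The formulas are: expected cases = 15p; P(at least one) = 1 − (1 − p)^15.

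| Item | p | Expected cases | P(at least one) |
|---|---|---|---|
| Tenderness | 0.01 to 0.10 | 0.15 to 1.5 | 14% to 79% |
| Induration | 0.0001 to 0.001 | 0.0015 to 0.015 | 0.15% to 1.5% |
| Nerve injury | up to 0.0001 | up to 0.0015 | up to 0.15% |

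Only tenderness is likely enough for the method to change what is reported.

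**4. Illustration for tenderness**

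If a fraction s of true cases is detected and p = 0.10, expected recorded cases are 1.5s and P(at least one recorded) = 1 − (1 − 0.10s)^15.

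| s | Expected recorded | P(at least one) |
|---|---|---|
| 1 | 1.5 | 79% |
| 0.75 | 1.125 | 69% |
| 0.50 | 0.75 | 54% |
| 0.25 | 0.375 | 32% |

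No value of s stands in the protocol. The table shows a range, not an estimate.

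**The case against.** The best defence is that the protocol does more than look. All eight reactions are named in frequent scheduled checks, so staff are alerted to each. Participants are asked for a pain score at six times after each dose, five of which coincide with site checks, and at 8 h they are asked how long any pain from IV or IM administration lasted. All adverse events are recorded through to the 48-hour call, which gives a symptomatic nerve injury a way into the data. Severity grading already applies to adverse events. Section 12.1 summarises measurements only as appropriate and tabulates adverse events separately, so an item without a mm value still has somewhere to go. The same check applies to IV and IM sites, and the safety analysis is descriptive.

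Much of this stands, and it narrows the point. It does not remove it. Naming an item within a visual check supplies no means of detecting it. The protocol treats pain and tenderness as separate endpoints. The pain score is not taken at the 15 to 60 min checks and is not specified per site, although the IM dose is given as two separate 5 mL injections (7.1.1).

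A reader might go further and infer that three-eighths of local reactions will be missed or left to spontaneous report, that inspection has practically no sensitivity for these items, or that IM tolerance will look better than it is. The documents support none of these. Three of eight is a count of list entries, not of expected events. No detection rate is given, firm induration may show as swelling, and pain is prompted. A bias in favour of IM is a plausible direction but is not shown.

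**Conclusion.** The point holds as a mismatch between a stated method and its endpoint. Sections 5.2, 5.3 and 10.2 fix a visual check with a mm reading for all eight reactions. That method cannot establish tenderness or nerve injury and is weak for induration. The list of elicited events contains nothing local, although the endpoint counts solicited local events. The consequence is a risk of under-ascertainment, in practice for tenderness, which the pain score offsets in part.

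The size of any bias cannot be derived from the documents. The illustrative figures rest on assumed frequency bands and assumed detection fractions. The conclusion that mainly tenderness is affected rests on the protocol's own ranking of tenderness as common, induration as rare and nerve injury as very rare. The primary pharmacokinetic objective is untouched. The text should be corrected because local safety by route is a stated objective and the correction is cheap.

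**What to change.** 1. In 5.2, 5.3 and 10.2, replace the visual-only wording with: *inspected and palpated, and the participant asked about tenderness and any numbness, tingling or weakness*. Keep the existing check times.
2. Record the longest diameter in mm for redness, swelling, induration and ecchymosis only. This also settles what is measured, since 10.2 asks for mm of a surface.
3. For tenderness, nerve injury, necrosis and infection, record presence and a severity grade using the CTCAE scale already adopted in 10.3.2. Record all items separately for each injection site.
4. Add the local items to the elicited list in 5.2 so that it matches the solicited local endpoint, and refer to that list at V3 and V5, where 5.3 does not repeat it.

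The cost is protocol wording, a few case report form fields and slightly longer checks by the same staff at visits already planned. No visits, samples or participants are added. More local reactions will be recorded, which should be expected when the results are read.

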10.3 Recording and reporting adverse events

10.3.1 Definitions

According to Article R1123-46 of the French Public Health Code:

- **Adverse event**

Any untoward medical occurrence in a trial subject, which does not necessarily have a causal relationship with the clinical trial or with the investigational product.

- **Adverse reaction to an investigational medicinal product**

Any adverse event occurred in a trial subject, which has a causal relationship with the clinical trial or with the investigational medicinal product

- **Serious adverse event or reaction**

Any adverse event or reaction that at any dose of medication, results in death, threatens the life of the research subject, requires hospitalisation or prolongs hospitalisation, causes a severe or long-term disability or handicap, or results in a congenital abnormality or deformity.

- **Unexpected adverse reaction to an investigational medicinal product**

Any adverse reaction to the product, whose nature, severity, frequency or outcome is inconsistent with the safety information described in the Reference Safety Information (summary of product characteristics, or the investigator's brochure if the product is not authorised).

According to Article R.1123-46 of the Code de la Santé Publique and the guidelines for clinical trial sponsors (ANSM):

- **Emerging safety issue**

Any new safety information that may lead to a reassessment of the risk/benefit ratio of the trial or the investigational medicinal product, modifications in the investigational medicinal product use, the conduct of the clinical trial, or the clinical trial documents, or a suspension, interruption or modification of the protocol of the clinical trial or other similar trials.

For the clinical trials involving the first administration or use of an investigational medicinal product in healthy volunteers, any serious adverse reaction.

Examples:

- a) any clinically significant increase in the frequency of an expected serious adverse reaction
- b) suspected unexpected serious adverse reactions in patients who have terminated their participation in the clinical trial that are notified by the investigator to the sponsor together with follow-up reports
- c) any new safety issue relating to the conduct of the clinical trial or the development of the investigational medicinal product, that may impact the safety of the trial subjects.

Examples:

- a serious adverse event likely to be related to the interventions and the trial's diagnostic procedures and which may impact the conduct of the clinical trial,

- a significant risk on the trial subjects such as ineffectiveness of the investigational medicinal product in treating a life-threatening illness under investigation,
- significant safety results from a recently completed non-clinical study (such as a carcinogenicity study),
- the premature termination, or temporary suspension, of a trial conducted on the same investigational medicinal product in another country, for safety reasons,
- an unexpected serious adverse reaction associated with a non-experimental medication required for the conduct of the clinical trial, (e.g. challenge agents, rescue treatment)

d) any suspected unexpected serious adverse reaction (SUSAR) reported to the sponsor by another sponsor of a trial carried out in a different country but relating to the same medication.

10.3.2 The role of the investigator

The investigator must **assess the seriousness criteria of each adverse event** and record all serious and non-serious adverse events in the case report form (eCRF).

The investigator must **document** serious adverse events **as thoroughly as possible** and provide a definitive medical diagnosis, if possible.

The investigator must **assess the severity** of the adverse events by using:

- Common Terminology Criteria for Adverse Events [National Cancer Institute]

The investigator must assess the **causal relationship** between the serious adverse events and the investigational medicinal product(s).

The method used by the investigator is based on the WHO Uppsala Monitoring Centre method and uses the following causality terms:

- Certain
- Probable/likely
- Possible
- Unlikely (not ruled out).

These terms are defined as follows (extracted from the WHO-UMC causality categories, version dated 17/04/2012).

Table 1: WHO-UMC causality categories (extract)

Causality term	Assessment criteria*
Certain	
 · Event or laboratory test abnormality, with plausible time relationship to drug intake ** · Cannot be explained by disease or other drugs · Response to withdrawal plausible (pharmacologically, pathologically) · Event definitive pharmacologically or phenomenologically (i.e. an objective and specific medical disorder or a recognized pharmacological phenomenon) · Rechallenge satisfactory, if necessary
Probable / Likely	
 · Event or laboratory test abnormality, with reasonable time relationship to drug intake** · Unlikely to be attributed to disease or other drugs · Response to withdrawal clinically reasonable · Rechallenge not required
Possible	
 · Event or laboratory test abnormality, with reasonable time relationship to drug intake ** · Could also be explained by disease or other drugs · Information on drug withdrawal may be lacking or unclear
Unlikely	
 · Event or laboratory test abnormality, with a time to drug intake ** · that makes a relationship improbable (but not impossible) · Disease or other drugs provide plausible explanations

*All points should be reasonably complied with

** Or study procedures

10.3.2.1 Serious adverse events that require a notification without delay by the investigator to the sponsor via AP-HP.

As per article R.1123-49 of the French Public Health Code (CSP), the investigator must notify the sponsor representative (APHP) **without delay on the day when the investigator becomes aware** of any serious adverse event which occurs during a trial as described in Article L.1121-1(1) CSP.

A serious adverse event is any untoward medical occurrence that:

- 1- results in death
- 2- is life-threatening
- 3- requires inpatient hospitalisation or prolongation of existing hospitalisation
- 4- results in persistent or significant disability/incapacity
- 5- is a congenital anomaly/birth defect

